4.2. Treatment Arms and Duration

This study will be conducted over a total duration of approximately 76 weeks: 16-week run-in period, 52-week double-blind treatment period and 8-week follow-up period. The study randomisation will be stratified by country.

Eligible subjects will receive a single-blind placebo inhaler during the 16-week run-in period. After completing the run-in period, eligible subjects will be randomly allocated to one of two treatment regimens:

- inhaled FF 50 mcg administered OD in the morning for 52 weeks

or

- inhaled placebo administered OD in the morning for 52 weeks

Each treatment will be administered via the ELLIPTA dry powder inhaler [formerly referred to as a novel dry powder inhaler (NDPI)].

Subjects will also receive open-label montelukast (4 mg for subjects who are 5 years old and 5 mg for subjects who are ≥ 6 years old). Subjects will take one tablet of montelukast each evening for the duration of the study (from the run-in period through to the end of the follow-up period). **Note:** subjects who turn 6 years old during the study, will subsequently receive 5 mg of open-label montelukast.

In addition, each subject will receive a short acting beta 2 agonist (SABA) (i.e., albuterol/salbutamol [inhalation aerosol or nebuliser]) to be used as needed throughout the entire study period as rescue medication for symptomatic relief of asthma symptoms.

Subjects (i.e., the child) **must** attend the clinic on the following visits for spirometry and other key assessments:

- **Visits 1 and 3 (Screening visit and run-in period):**
 - Visit 1, subjects will attend the clinic for screening procedures. Subjects meeting the eligibility criteria will enter the 16-week run-in period.
 - Visit 3, subjects will attend the clinic for spirometry assessment and any other assessments as indicated in the Time and Events Table (Section 7.1).
- **Visit 5 (Randomisation):**
 - Eligible subjects will be randomised to one of two treatment groups.
 - Subjects will attend the clinic for spirometry assessments and any other assessments as indicated in the Time and Events Table (Section 7.1).
- **Visits 6, 7, 8, 9, 12, 15 and 18 (Double-blind treatment period)**
 - Subjects will attend the clinic for spirometry assessments and any other assessments as indicated in the Time and Events Table (Section 7.1).
- **Visit 20 (Follow-up period)**

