6. STUDY TREATMENT

6.1. Investigational Product and Other Study Treatment

The term ‘study treatment’ is used throughout the protocol to describe any combination of products received by the subject as per the protocol design. Study treatment may therefore refer to the individual study treatments or the combination of those study treatments.

	Study Treatment		
Product name:	FF (GW685698) 50mcg Dry Powder Inhaler*	Placebo*	Montelukast (open label)
Formulation description:	Dry Powder Inhaler	Dry Powder Inhaler	4 mg chewable tablet (5 year old subjects) 5 mg chewable tablet (≥6 year old subjects) Note: subjects who turn 6 years old during the study, will subsequently receive 5 mg of open-label montelukast.
Dosage form:	Dry Powder Inhaler	Dry Powder Inhaler	Chewable tablet
Unit dose strength(s)/Dosage level(s):	50 mcg per blister	Lactose	4 mg or 5 mg
Route of Administration	Inhaled	Inhaled	Oral
Dosing instructions:	Inhale once daily in the MORNING	Inhale once daily in the MORNING	Once daily in the EVENING
Physical description:	Dry White Powder	Dry White Powder	Chewable tablet
Storage conditions	Store up to 25°C (77°F)	Store up to 25°C (77°F)	Per commercial Label: 59°F to 86°F (15°C to 30°C).
Device:	ELLIPTA	ELLIPTA	N/A
Method for individualizing dosage:	Inhalation (oral)	Inhalation (oral)	Chewable tablet

*Single Strip

During the run-in period, all eligible subjects will receive a single-blind placebo ELLIPTA inhaler.

Each subject will also receive an albuterol/salbutamol (inhalation aerosol or nebuliser) to be used as needed throughout the entire study period as rescue medication for symptomatic relief of asthma symptoms.

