7.4. Efficacy (as a Measure of Compliance)

7.4.1. Daily Diaries

Subjects/parents/guardians will be issued an eDiary for daily use throughout the study and will be instructed on how to complete the eDiary. As well as recording compliance with study medication (single-blind treatment during the run-in period, double-blind treatment and open-label montelukast) in the eDiary, the following parameters will be recorded used as a measure of compliance to help identify non-adherence and/or poorly controlled asthma:

- Daily asthma symptom scores
- Daily PEF (measured in the morning only)
- Daily albuterol/salbutamol use. Number of inhalations of rescue albuterol/salbutamol inhalation aerosol used during the day and night.
Note: Rescue medication taken as preventative treatment before exercise will be excluded from this count and should not be entered into the daily eDiary.

[figure not shown]
If a subject discontinues study treatment, the subject should be encouraged to remain in the study and continue to follow the regular visit schedule. However, the subject will no longer be required to complete the eDiary.

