5.2. Baseline Definitions

In general, the baseline study period will be defined as an aggregate of measurements recorded during the period between screening and randomisation (Visits 1 – 5). Specific details follow below.

Baseline growth velocity

Each participant's baseline growth velocity (cm/yr) will be calculated based on the stadiometric height measurements recorded at Visits 1, 3, and 5. These data will be used to fit a simple linear regression line against time. The slope of the fitted regression line will be the participant's baseline growth velocity. Note that baseline growth velocity will be derived if there are baseline stadiometric height assessments from at least two clinic visits. Otherwise baseline will be missing.

Baseline height standard deviation score (SDS)

Each participant's Visit 5 height standard deviation score will serve as the baseline height SDS. Height standard deviation scores will be calculated as described in Section 11.6.3.

Baseline eDiary measures

Baseline PEF will be defined as the average of the measurements recorded on the morning of randomisation (Visit 5) and on the previous 6 days.

The average daily rescue medication used over the last 7 days prior to randomisation, including the rescue medication use recorded on the morning of randomisation, will be used as the baseline value.

The baseline percentage of rescue-free 24-hour periods will be defined as the percentage of 24-hour periods in the 6 days prior to randomisation and on the day of randomisation in which a participant used no rescue medication. Percentage rescue-free 24-hour periods will be calculated as described in Section 11.6.5.

The baseline percentage of symptom-free 24-hour periods will be defined as the percentage of 24-hour periods in the 6 days prior to randomisation and on the day of randomisation for which a participant's daytime asthma symptom score and night-time symptom score is 0. Percentage symptom-free 24-hour periods will be calculated as described in Section 11.6.5.

Baseline C-ACT score

Each participant's Visit 5 C-ACT score will serve as the baseline score.

Derivations and handling of missing baseline data

If the baseline for an endpoint is missing it will not be imputed using a different time point or derivation but will remain missing. For example, if there is no C-ACT value available at Visit 5, then baseline C-ACT will be missing.

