11.6.5. Efficacy

eDiary
Rescue-Free 24-Hour Periods

 Rescue medication use over the previous 24 hours is recorded in the eDiary each morning. Therefore, rescue medication use recorded on study day n refers to actual use on study day $(n - 1)$. A given 24-hour period will only be set to “rescue free” if responses to the daily assessment of rescue medication use is 0. Any >0 values will require that the 24-hour period be marked as not rescue-free. If the assessment of rescue medication use in a given 24-hour period is missing, then the “rescue-free” indicator will also be set to missing. Percentages of rescue-free 24-hour periods are calculated as the number of 24-hour periods on which a participant recorded no use of albuterol/salbutamol divided by the length of the time period being assessed (with non-missing values of rescue medication recorded) x 100. See Section 11.7.2 for determination of rescue-free 24-hour periods and handling of missing data.
Symptom-Free 24-Hour Periods

 Daytime symptoms, reflective of the participant’s state during the previous day, are collected in the morning. Similarly, overnight symptoms are recorded the following morning. Therefore, daytime and nighttime symptoms recorded on study day n refer to the participant’s symptoms on study day $(n - 1)$. A given 24-hour period will only be set to “symptom free” for a given 24-hour period if responses to both the morning and evening asthma symptom scores are 0. Any >0 values in either the morning or evening assessment will require that the 24-hour period be marked as not symptom-free. If either the morning or evening assessment asthma symptom score in a given 24-hour period is missing, then the “symptom-free” indicator will also be set to missing. Percentages of symptom-free 24-hour periods are calculated as the number of 24-hour periods on which a participant recorded no symptoms divided by the length of the time period being assessed (with non-missing values of symptoms recorded) x 100. See Section 11.7.2 for determination of symptom-free 24-hour periods and handling of missing data.
Peak Expiratory Flow (PEF)
Peak expiratory flow (PEF) is recorded in the morning, thus a PEF measurement recorded on study day n is associated with study day n .

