Symptom Scores		24-hour Period																																								
AM	PM																																									
>0	0	Not symptom-free																																								
0	>0	Not symptom-free																																								
0	0	Symptom-free																																								
0	Missing	Missing																																								
Missing	0	Missing																																								
>0	Missing	Not symptom-free																																								
Missing	>0	Not symptom-free																																								
Missing	Missing	Missing																																								
Rescue medication use (puffs)																																										
0		Rescue-free																																								
>0		Not rescue-free																																								
Missing		Missing																																								

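### The rescue diary item counts only aerosol inhalations although rescue may also be nebulised, so as written a day with nebulised rescue alone is scored rescue-free

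*Protocol*

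**What the plan says.** **Rescue supplied.** Protocol 6.1 gives each child "albuterol/salbutamol (inhalation aerosol or nebuliser) to be used as needed throughout the entire study period as rescue medication". Protocol 1 and 4.2 and SAP 2.3 name the same two forms. Protocol 6.10.2 and 7.2 also name both when rescue has to be withheld before the screening FEV₁.

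**What the diary counts.** Protocol 7.4.1 defines the daily rescue item as "Number of inhalations of rescue albuterol/salbutamol inhalation aerosol used during the day and night", and SAP 9 repeats the definition. The only use expressly left out of the count is preventive use before exercise.

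**How a day is scored.** Under SAP 11.6.5 a 24-hour period is rescue-free only "if responses to the daily assessment of rescue medication use is 0". The scoring table in SAP 11.7.2 is in puffs: zero is rescue-free, more than zero is not rescue-free, and a missing entry is missing.

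**What the endpoint is meant to be.** SAP 11.6.5 describes the numerator of the percentage as "the number of 24-hour periods on which a participant recorded no use of albuterol/salbutamol". SAP 5.2 describes baseline in terms of periods "in which a participant used no rescue medication". Neither is limited to one form of the drug.

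**Its place in the plan.** Change from baseline in this percentage is an Other endpoint (Protocol 3). It serves as a measure of compliance, to help find non-adherence or poorly controlled asthma. SAP 9.1 plans summaries by treatment and no formal analysis.

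**The concern.** The count covers one of the two permitted forms of rescue, while the endpoint is described as covering all of it. No section says how a nebulised dose is entered, converted to puffs or scored. A parent who gives a nebulised treatment and no puffs, and who follows the written definition, enters zero, and the SAP then scores that day as rescue-free.

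On any recorded day the error goes one way: a day with rescue is called a day without it. A child who used only the nebuliser would show 100% rescue-free periods however often rescue was given. The diary measures are kept partly to flag poorly controlled asthma, and the rescue item would give no signal in such a child.

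**Working it through.** The plan states no figure for this endpoint, so there is none to reproduce. The check applies the written scoring rule to each kind of day and then finds what one misclassified day is worth.

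**Step 1: apply the rule in SAP 11.7.2.**

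| Puffs entered | Nebuliser used | Score under the SAP | Correct for no rescue used? |
|---|---|---|---|
| 0 | no | rescue-free | yes |
| 0 | yes | rescue-free | **no** |
| 2 | no | not rescue-free | yes |
| 2 | yes | not rescue-free | yes |
| missing | yes | missing | not scored |

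Only days on which the nebuliser was the sole rescue are misclassified.

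**Step 2: value of one such day.** SAP 11.6.5 divides by the number of periods with a rescue entry. With k nebuliser-only days among L recorded days, the percentage is too high by

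e = 100 × k / L.

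Inputs: L = 7 at baseline (SAP 5.2: the 6 days before randomisation and the day itself), and L = 52 × 7 = 364 over the treatment period with a complete diary.

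- Baseline, k = 1: 100 × 1/7 = 14.29 points.
- Treatment, k = 1: 100 × 1/364 = 0.27 points.
- Treatment, k = 5: 100 × 5/364 = 1.37 points.
- Treatment, k = 10: 100 × 10/364 = 2.75 points.

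Incomplete diaries make L smaller and each day worth more.

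**Step 3: carry this to the endpoint, which is a change.** The same rule scores both windows, so

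error in change = e(treatment) − e(baseline) = 100 × (k_T/L_T − k_B/L_B).

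| Nebuliser-only days, baseline (of 7) | Nebuliser-only days, treatment (of 364) | Error in change (points) |
|---|---|---|
| 1 | 0 | 0 − 14.29 = −14.29 |
| 0 | 10 | 2.75 − 0 = +2.75 |
| 1 | 52 | 14.29 − 14.29 = 0 |

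The first child's improvement is understated and the second child's change is overstated. In the third child the rate is one day in seven throughout, and the errors cancel. The counts of days are illustrations, because the documents give no frequency of nebuliser use.

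**The case against.** The strongest reply is that nobody reading these documents has seen the instrument. The eDiary screens are not included. Other descriptions of the item are broader: the Protocol 7.4.1 bullet opens with daily albuterol/salbutamol use in general, the footnote to the Time and Events Table (Protocol 7.1) speaks of daily salbutamol use, and SAP 11.6.5 speaks of rescue medication use over the previous 24 hours. Families are to be instructed in completing the diary. A device that takes a nebulised dose as a non-zero entry would fit all of these. This stands in part: whether any day was misclassified is unknown. It does not remove the point, because the two sections that define the count restrict it to the aerosol, the scoring table is in puffs, and nothing tells a parent or programmer to do otherwise.

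The second reply is that little depends on this endpoint. That stands. It is descriptive, and control is also followed through symptom scores, daily PEF with an alert at the stability limit, C-ACT and the exacerbation log.

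Three stronger readings are tempting, and the documents do not support them.

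- A reader might infer that the arm means, or the difference between arms, are biased by some number of points. That would need the frequency of nebuliser-only days by arm and by period, and no section gives it. An error in the level is also not an error in the change.
- A reader might infer that the trial loses its evidence that FF was taken. Adherence is measured directly, by the ELLIPTA dose counter and the daily diary question (Protocol 6.7; SAP 11.6.2).
- A reader might infer that the days could be rescored from other records. No section says that as-needed doses of study rescue are dated in the concomitant-medication log, and SAP 11.7.2.1 imputes partial start dates there to the first of the month or to January. The exacerbation log covers only exacerbations as defined in Protocol 7.3.3. No section says that the form of rescue dispensed is recorded.

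**Conclusion.** The point holds as a mismatch between the written count and the endpoint's stated concept. If the rule is followed, a nebuliser-only day is scored rescue-free. This is more than missing detail, because the stated rule gives a wrong result in a situation that the protocol expressly allows.

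The effect on an individual child's change from baseline can be large, because a single day in the short baseline window moves it by more than any plausible handful of treatment days. It can go either way. The effect on arm summaries cannot be stated from the documents. The per-day sizes assume complete diaries and a parent who enters zero after nebulised rescue alone.

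The reach is limited. Growth velocity is computed from stadiometry and does not use the diary, so the primary analysis is untouched.

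**What to change.** - **Protocol 7.4.1 and SAP 9:** define the item as any rescue albuterol/salbutamol, recorded as the number of puffs and the number of nebulised treatments, and keep the existing pre-exercise exclusion.
- **SAP 11.6.5 and 11.7.2:** define a 24-hour period as rescue-free only if both counts are zero, and as not rescue-free if either is above zero. State how a period is scored when one count is zero and the other is missing; treating it as missing would match the existing rule for symptom scores.
- **If the eDiary can no longer be changed:** state in the SAP, before unblinding, how nebulised doses were entered. If they were not captured, label the endpoint as aerosol-rescue-free periods in the text and in Table 3.1, so that readers do not take it as freedom from all rescue.

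The cost is one diary field and a two-line scoring rule, or otherwise one sentence and a relabelled table. The change concerns recording and scoring only and leaves rescue treatment as it is. Rescue-free percentages may come out somewhat lower.

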7.4.1.1. Daily Asthma Symptom Scores

The following asthma symptom scores will be recorded once daily in the morning in the eDiary before taking any study treatment, before using any rescue medication, and before the daily PEF measurement:

[figure not shown]
Day-time Symptom Score for previous day:

CCI - This section contained Clinical Outcome Assessment data collection questionnaires or indices, which are protected by third party copyright laws and therefore have been excluded.

Night-time Symptom Score:

CCI - This section contained Clinical Outcome Assessment data collection questionnaires or indices, which are protected by third party copyright laws and therefore have been excluded.

7.4.1.2. Daily PEF

PEF will be measured daily in the morning using an electronic Peak Flow Meter that will be issued to subjects at Visit 1. The best of three attempts will be recorded by the subjects in the eDiary.

PEF will be measured and recorded daily throughout the study. PEF measurements must be done:

- Each morning prior to taking any study treatment and before using any rescue medication.

For all randomised subjects, a PEF Stability Limit will be calculated as follows:

- Mean PEF from the available 7 consecutive days preceding Visit 2 (during run-in period) x 60%.

- The PEF from the morning of Visit 2 will be included in the calculation of the PEF stability limit.

Subjects will be alerted if their PEF has fallen below the PEF Stability Limit.

7.4.2. Childhood Asthma Control Test

The Childhood Asthma Control Test (C-ACT) will be assessed at scheduled visits outlined in the Time and Events Table.

The C-ACT is a 7-item questionnaire which has been developed as a measure of paediatric subjects' (4-11 years old) asthma control [Liu, 2007], and which can be quickly and easily completed in clinical practice. It is designed for completion by the subject and by the subject's parent/legal guardian. The subject (child) should complete questions 1-4 as independently as possible; however, if a child has difficulty with completion, the parent/legal guardian can provide assistance. The parent/legal guardian should complete questions 5-7 without letting their child's responses influence their answers. The investigator or designated study site personnel should encourage the patient not to skip questions on the C-ACT or take breaks during the completion of the paper questionnaire. Responses to questions should not be changed or modified after collection. Upon completion of the C-ACT, the investigator or designated site personnel will collect the questionnaire and calculate the total score. The C-ACT responses will be administered and recorded in the CRF by the investigator or delegate.

7.5. Genetics

Information regarding genetic research is included in [Appendix 3](#).

8. DATA MANAGEMENT

- For this study subject data will be entered into electronic case report forms (eCRFs), transmitted electronically to GSK or designee and combined with data provided from other sources in a validated data system.
- Management of clinical data will be performed in accordance with applicable GSK standards and data cleaning procedures to ensure the integrity of the data, e.g., removing errors and inconsistencies in the data.
- Adverse events and concomitant medications terms will be coded using MedDRA (Medical Dictionary for Regulatory Activities) or alternative, and a validated medication dictionary (e.g. GSKDrug).
- CRFs (including queries and audit trails) will be retained by GSK or designee, and copies will be sent to the investigator to maintain as the investigator copy. Subject initials will not be collected or transmitted to GSK according to GSK policy.

9. STATISTICAL CONSIDERATIONS AND DATA ANALYSES

9.1. Hypotheses

The primary objective of this study is to characterise the estimated difference in prepubescent growth velocities between subjects treated for one year with inhaled FF 50 mcg once daily (OD) (plus montelukast 4mg or 5mg open-label) and inhaled placebo (plus montelukast 4mg or 5mg open-label).

No formal statistical hypotheses are to be tested.

9.2. Sample Size Considerations

9.2.1. Sample Size Assumptions

The proposed sample size for this study is based on FDA guidance [[Guidance for Industry Orally Inhaled and Intranasal Corticosteroids: Evaluation of the Effects on Growth in Children](#), March 2007].

The study is not powered to detect any treatment differences. The study is designed to provide the estimated mean treatment difference between inhaled FF 50 mcg once daily (OD) (plus montelukast open-label) and inhaled placebo (plus montelukast open-label) in prepubescent growth velocities, with a certain degree of precision on the 95% confidence interval. The primary population for growth analyses will be the Growth Population (defined in Section 9.3.1). An analysis of covariance (ANCOVA) model will be used to estimate the mean treatment difference in growth velocities over the double-blind treatment period, adjusting for baseline growth velocity, age at Visit 1, gender, and country. A 95% confidence interval will also be provided for the estimated mean treatment difference in growth velocity over the double-blind treatment period (Section 9.4.1).

Eligible subjects will be stratified by country and randomised in a 1:1 ratio to inhaled FF 50 mcg OD (plus montelukast open-label) or inhaled placebo (plus montelukast open-label). At least 450 subjects will be randomised (approximately 225 per treatment arm). Assuming a withdrawal rate from study medication of up to 10% within the first 12 weeks, this would still ensure at least 406 eligible subjects (approximately 203 per treatment arm) for inclusion in the Growth Population (Section 9.3.1) analyses. Assuming a standard deviation for the growth velocities of 1.2 cm/year (based on study FFR101782), a sample size of 203 eligible subjects per treatment arm ensures the width of the confidence interval for the mean treatment difference is no greater than 0.5cm/year (Section 9.2.2).

